6.1.4.3 Concomitant Antibiotic Therapy

Subjects who receive any systemic concomitant antibiotic therapy from the time of the first dose of test article through the time of the last dose of test article at EOT and through the PTE Visit with a spectrum of activity against the known or potential infecting pathogen(s) responsible for the CABP under study will be excluded from the CE-EOT and CE-PTE populations, respectively, unless the subject receives the antibiotic therapy for treatment of the CABP due to insufficient therapeutic effect of the test article (ie, for progression or development of new symptoms of CABP or development of infectious complications of CABP).

Subjects who receive a systemic concomitant antibiotic that is not effective against the baseline pathogen, or if no pathogen is isolated, and the antibiotic does not have activity against CABP pathogens, will be included in the CE-EOT and CE-PTE populations.

6.1.4.4 Test Article Therapy

Subjects must meet all of the following to be included in the CE populations:

- Received at least 1 dose of active test article and the correct test article based on the randomization assignment.
- Study personnel involved in the assessment of efficacy remained blinded to study treatment, unless a treatment limiting adverse event (AE) occurred which required emergency unblinding.
- Evaluable failure: The subject received the first 2 doses (if receiving 200 mg iv QD on Day 1) or 3 doses (if receiving 100 mg iv on Day 1) of active test article (omadacycline group) or first 2 doses of active test article (moxifloxacin group) and the investigator classifies the subject as a Clinical Failure at the EOT Visit (CE-EOT population) or the overall Clinical Response (based on the investigator's assessment) at the PTE Visit (CE-PTE population) is Clinical Failure.
- Evaluable success: The subject received the first 3 doses (if receiving 200 mg iv QD on Day 1) or 4 doses (if receiving 100 mg iv on Day 1) of active test article (omadacycline group) or the first 3 doses of active test article (moxifloxacin group) and the investigator classifies the subject as a Clinical Success at the EOT Visit (CE-EOT population) or the overall Clinical Response (based on the investigator's assessment) at the PTE Visit (CE-PTE population) is Clinical Success.

6.1.4.5 Clinical Outcome Assessment

Subjects must meet the following to be included in the CE populations:

- For the CE-EOT population:
 - Completed the investigator's assessment of clinical response (ie, was not deemed an indeterminate outcome) at the EOT Visit, and
 - The EOT Visit occurred on the day of, or within 2 days following the last dose of test article.
- For the CE-PTE population:
 - The overall Clinical Response (based on the investigator's assessment) at the PTE Visit is not Indeterminate.
 - The PTE Visit occurred 5 to 10 days after the last dose of test article, unless the subject was considered to be a Clinical Failure based on the investigator's assessment at the EOT Visit or the patient died after EOT and before PTE.

6.1.4.6 Baseline Medical Events

Subjects will be excluded from the CE populations if the investigator has documented in the eCRF that they meet any one of the following protocol-defined exclusion criteria at baseline (ie, prior to randomization):

Exclusion Criterion 2: Is known or suspected to have CABP caused by a pathogen that may be resistant to either test article (eg, , *Pseudomonas aeruginosa*, *Proteus* spp., *Morganella morganii*, *Providencia* spp. *Pneumocystis jiroveci*, obligate anaerobes, mycobacteria, fungal pathogens).

Exclusion Criterion 3: Suspected or confirmed empyema (a parapneumonic pleural effusion is not an exclusion criteria) or lung abscess.

Exclusion Criterion 5: Subjects who reside in a long-term care or subacute/intermediate healthcare facility (eg, nursing home) or a subject admitted with pneumonia following a recent hospitalization (overnight admission within 90 days prior to current admission.

Exclusion Criterion 12: Requires acute pharmacologic intervention to stabilize blood pressure (BP) and/or adequate tissue perfusion, OR meets septic shock criteria (meets ALL of the following):

- Meets at least 2 criteria for sepsis as defined by the quick Sequential Organ Failure Assessment (qSOFA) score: (a) Altered mental status with Glasgow Coma Scale (GCS) < 15, (b) RR ≥ 22 breaths per minute, and (c) SBP ≤ 100 mmHg
- Despite adequate fluid resuscitation, persistent hypotension requiring vasopressors to maintain mean arterial pressure (MAP) ≥ 65 mmHg.
 - Serum lactate $\geq 2 \text{ mmol/L}$ (serum lactate measurement is not required at

Screening if any of the above septic shock criteria are not met)

Exclusion Criterion 13: PORT Risk Class I, II and V patients.

1. Exclusion Criterion 14; Requires or expected to require Intensive Care Unit (ICU) admittance or invasive or non-invasive ventilation.

Exclusion Criterion 15: Known or suspected primary or metastatic neoplastic lung disease, aspiration pneumonia, active tuberculosis, cystic fibrosis, bronchiectasis, bronchial obstruction (eg, post-obstructive pneumonia), chronic neurological disorder preventing clearance of pulmonary secretions, or severe chronic obstructive pulmonary disease (COPD) (severe COPD is defined as known forced expiratory volume in 1 second [FEV1] < 50% of predicted in a patient with FEV1/forced vital capacity [FVC] < 70%; note that spirometry or pulmonary function testing is not required during Screening).

6.1.5 Microbiologically Evaluable (ME) Populations

The ME-EOT and ME-PTE populations will consist of all subjects in both the microITT and the CE-EOT and CE-PTE populations, respectively.

6.2 Evaluability Review Team

6.2.1 Membership and Responsibilities

The Evaluability Review Team (ERT) will review both clinical and microbiological data for determination of criteria used to assess inclusion in the analysis populations and for determination of baseline and post-baseline pathogens. ERT members will be blinded to treatment assignment and will review the data concurrent with the conduct of the study. The ERT will be conducted in accordance with the ERT Process Document.

6.2.2 **Process for Determining Inclusion in Populations**

Inclusion into the ITT and Safety populations will be determined programmatically from the eCRF data. Inclusion into the CE populations will be determined programmatically from the eCRF data and the manual review conducted by the ERT. The ERT may review subject data to confirm that population criteria are satisfied.

Inclusion into the microITT population will be determined programmatically by incorporating the outcome of the review of the isolates by the ERT. The ERT will determine whether each isolate (baseline and post-baseline) is considered a pathogen based on a review of information from baseline samples including Gram stain results, and local and central laboratory genus and species identification. Inclusion into the ME populations will be determined programmatically.

Review of data, Sponsor determination of evaluability, and final subject population classification will be performed in a blinded manner prior to database lock and unblinding with the exception of those criteria requiring the subject's actual treatment assignment (for example, the requirement for the subject to have received the correct test article per the randomization assignment). For the criteria requiring the subject's actual treatment assignment assignment, population determination will be completed programmatically.

6.3 Subgroups

Analyses will be conducted (as described in Section 9) for subgroups defined by the randomization stratification factors: PORT Risk Class (III and IV) and receipt of an allowed antibacterial therapy in the 72 hours prior to study treatment (yes vs no). Analyses of ECR (in the ITT population) and clinical response at the PTE visit (in the ITT and CE-PTE populations) will also be conducted in the following subgroups: bacteremic subjects, defined as subjects with a positive blood culture at baseline (microITT population), by CURB-65 Score, and subjects meeting the systemic inflammatory response syndrome (SIRS) criteria at baseline. CURB-65 Score is derived from the eCRF data and ranges from 0-5 where 1 point is given for each of the following at baseline: confusion, blood urea nitrogen > 19 mg/dL (urea > 6.8 mmol/L), respiratory rate \geq 30 breaths/min, systolic blood pressure < 90 mmHg or diastolic blood pressure \leq 60 mmHg, and age \geq 65 years. Confusion is defined as altered mental status as recorded on the PORT Risk Class Determination eCRF. SIRS is defined as having 2 or more of the following criteria: temperature < 36°C or > 38°C (oral or oral equivalent), heart rate > 90 bpm, respiratory rate > 20 breaths/min, or WBC count < 4000 cells/mm³ or > 12,000 cells/mm³ or > 10% bands.

Exploratory analyses in other subgroups may also be conducted.

7 OVERALL STATISTICAL CONSIDERATIONS

7.1 General Conventions

The following general comments apply to all statistical analyses and data presentations:

- Summaries will include frequency and percentages for categorical data; frequency and median for ordinal data; and frequency, mean, standard deviation, and median, minimum, and maximum for quantitative data.
- Duration variables will be calculated using the general formula (end date start date) +1.
- Change from baseline will be calculated for each subject at the specified time point as the value at the specified time point minus the baseline value.
- If the reported value of a clinical laboratory parameter cannot be used in a statistical summary table (eg, a character string is reported for a parameter of the numerical type), a coded value must be appropriately determined and used in the statistical analyses. In general, a value or lower and upper limit of normal range such as '< 10' or '≤ 5' will be treated as '10' or '5' respectively, and a value such as '> 100' will be treated as '100.' However, the actual values as reported in the database will be presented in data listings. Data will be reviewed on an ongoing basis in a blinded manner to assess the frequency of occurrence of laboratory parameters reported as a character string.
- Individual subject listings of all data represented on the eCRFs will be provided to facilitate the investigation of tabulated values and to allow for the clinical review of all efficacy and safety parameters.
- Version 9.3 (or higher) of SAS® statistical software package will be used to provide all summaries, listings, graphs, and statistical analyses.

7.2 **Baseline Definition**

In general, baseline is defined as the value closest to but prior to the initiation of test article administration. If no test article is received, baseline is defined as the value closest to but prior to randomization.

For pathogen determination, baseline is defined as either Day -1 or 1 (the 24-hour period prior to the administration of the first dose of test article) or if the subject is unable to produce a sputum sample at baseline or the sputum sample does not have an adequate Gram stain, a specimen obtained within 24 hours after the first dose of test article may be used as baseline. If no test article is received, for pathogen determination, Study Day is defined based on date of randomization.

For analyses of vital signs and ECGs, if no value is available prior to the initiation of test article administration, a value within 2 hours after initiation of test article administration can be used as baseline.

7.3 Handling of Missing Data

Missing data will be handled as outlined below:

- All missing and partial dates for AEs or for medications received after randomization will be queried for a value. If no value can be obtained, substitutions will be made as detailed in Appendix 3. These substitutions will be used in calculations; however, the actual value recorded on the eCRF will be used in all listings.
- Missing start and stop times for prior and concomitant antibiotics will be queried for a value. If no value can be obtained but the site indicates the antibiotic was received (onset time) prior to the first dose of test article, 00:01 will be used for the onset time. If the site also indicates that the end time was prior to the first dose of test article, 00:01 will be used for end time. The actual value (blank) will be recorded on the eCRF and will be used in the listings.
- Missing times for assessments of CABP symptoms will be queried for a value. If minutes are not available, the time will be recorded to the closest hour.
- If no value can be obtained for all other times for events and assessments occurring after randomization, the time will not be imputed but will remain missing.
- The severity and causality assessment for AEs cannot be missing. Missing data will be queried for a value.
- If the time of administration of the first dose of test article is missing, it will be set to 1 minute after midnight (00:01)

For clinical and microbiological response, missing data will be handled as follows:

- For the primary outcome measure (ECR at 72 to 120 hours after administration of the first dose of test article):
 - The subject will be considered to have missing data if an assessment of all of the CABP symptoms (cough, sputum production, pleuritic chest pain, and dyspnea) is not made from 72 to 120 hours after the administration of the first dose of test article, unless the subject is considered a Clinical Failure for another reason. Subjects who do not have at least 2 symptoms of CABP at baseline will also be considered to have missing data unless the subject is considered a Clinical Failure for another reason. Subjects with missing data will be defined as an Indeterminate response which is essentially a Clinical Failure for the primary analysis in the ITT population.
- For the secondary outcome measures (investigator's assessment of Clinical Response at the EOT and PTE Visits):
 - Subjects will be defined as an Indeterminate if the investigator cannot determine whether the subject is a Clinical Success or Failure at the EOT or PTE Visits or the subject has a missing response Table 4. By definition, subjects with an Indeterminate response are included in the denominator for analyses in the ITT and microITT populations, and thus, are considered Clinical Failures. Subjects with an

Indeterminate response are excluded from the CE-EOT, CE-PTE, ME-EOT and ME-PTE populations.

- For microbiologic response:
 - If no post-baseline source specimen is obtained and the subject has an investigator's assessment of Clinical Response, the per-pathogen microbiological response is based on the investigator's assessment of Clinical Response (ie, the response is a presumed response). A per-pathogen microbiological response at the EOT Visit or PTE Visit will be considered Indeterminate only if the Clinical Response at EOT or PTE is also Indeterminate.
- Missing values for other individual data points will remain as missing. Missing values will not be imputed and only observed values will be used in data analyses and presentations.
- Where individual data points are missing, categorical data will be summarized based on reduced denominators (ie, only subjects with available data will be included in the denominators).

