## 12.16 Handling of Missing Values/Censoring/Discontinuations

Missing values will not be imputed for primary and secondary efficacy and safety analyses (except as detailed in the SAP for missing dates) and only observed values will be used in data analyses and presentations. For the primary outcome measure of ECR, if any data field needed to determine the response is missing the subject will be assigned an Indeterminate response. Subjects with an Indeterminate response are included in the denominator, and thus, are considered Clinical Failures. A sensitivity analysis of the primary outcome of ECR will be conducted in which subjects with an Indeterminate response are considered Clinical Successes.

For the EMA primary outcome measure of Investigator's Assessment of Clinical Response at PTE in the ITT population (secondary outcomes for FDA), subjects with missing data are assigned an Indeterminate response. Subjects with an Indeterminate response are included in the denominator, and thus, are considered failures. Table 6 provides a summary of the handling of missing/indeterminate outcomes for the Investigator's Assessment of Clinical Response at PTE.

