The categories of Early Clinical Response are defined as follows:

Clinical Success: at the ECR assessment will be defined as survival with improvement of at least 1 level (ie, severe to moderate, moderate to mild, mild to absent) compared to baseline (Screening) in at least 2 CABP symptoms (cough, sputum production, pleuritic chest pain, and dyspnea) with no worsening by at least 1 level in the other CABP symptoms. In order for the subject to be considered a Clinical Success, the subject may not meet any criteria for Clinical Failure or Indeterminate ECR.

Clinical Failure: meeting any of the following criteria:

• There is no improvement by at least 1 level (ie, severe to moderate, moderate to mild, mild to absent) compared to baseline (Screening) in 2 CABP symptoms.

- Any of the 4 CABP symptoms is worse (by at least 1 level) compared to baseline (Screening).
- The subject requires alternative (rescue) antibacterial treatment for CABP prior to the ECR assessment related to either (a) progression or development of new symptoms attributable to CABP; (b) development of infectious complications of CABP (eg, empyema, lung abscess) or (c) discontinuation of study therapy due to an AE.
- The subject is receiving antibacterial therapy that may be effective for the infection under study for a different infection from the one under study.
- Death prior to the ECR assessment.

Indeterminate: the clinical response to test article could not be adequately inferred due to:

- Subject was not seen for the evaluation because s/he withdrew consent, or were lost to follow-up
- Other specified reason.

Assuming none of the above definitions of failure is met, the following cases will be considered an indeterminate response: Subjects with missing data such that an ECR Response cannot be determined; subjects who did not have at least 2 symptoms of CABP at baseline; subjects with an ECR assessment outside of the 72–120-time window. Since subjects with an indeterminate response are included in the denominator of the calculation of Clinical Success, these subjects are essentially Clinical Failures. For the ITT population, the proportion of ITT subjects with a Clinical Success is defined using the following formula:

Number of subjects with an Early Clinical Success

Number of subjects with an Early Clinical Failure + Number of subjects with a response of Indeterminate + Number of subjects with an Early Clinical Success

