- The subject requires alternative antibacterial treatment for CABP prior to PTE related to either:
 - o progression or development of new symptoms of CABP, or
 - o development of infectious complications of CABP (eg, empyema, lung abscess).

Other reasons for clinical failure are:

- The subject is receiving antibiotics that may be effective for the infection under study for a different infection from the one under study.
- Death prior to PTE.

Indeterminate:

• The clinical response to test article could not be adequately inferred due to:

- Subjects were not seen for PTE evaluation because they withdrew consent, were lost to follow-up, other (specify).
- Other specified reason.

The efficacy outcome of Clinical Response at PTE is determined as follows from the investigator's assessments at the EOT and PTE Visits:

Table 4.Investigator's Assessment of Clinical Response

EOT Visit	PTE Visit	Clinical Response at PTE Visit
Success	Success	Success
Success	Failure	Failure
Success	Indeterminate	Indeterminate
Failure	Success	Failure
Failure	Failure	Failure
Failure	Indeterminate	Failure
Indeterminate	Success	Indeterminate
Indeterminate	Failure	Failure
Indeterminate	Indeterminate	Indeterminate

Abbreviations: EOT = end of treatment; PTE = post-therapy evaluation.

For the ITT population, the proportion of ITT subjects with a Clinical Success is defined using the following formula (where the denominator adds to the total number of subjects in the ITT population):

Number of subjects with Clinical Success

(Number of subjects with Clinical Success + Number of subjects with a Clinical Failure + Number of subjects with an Indeterminate response)

By definition, subjects in the CE-EOT and CE-PTE populations cannot have an Indeterminate response. Thus, for the CE-EOT and CE-PTE populations, the proportion of subjects with a Clinical Success is defined using the following formula:

Number of subjects with Clinical Success

(Number of subjects with Clinical Success + Number of subjects with a Clinical Failure)

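### A subject not failed at EOT who is rescued for CABP or dies before PTE, with no PTE response recorded, becomes Indeterminate and drops out of CE-PTE and ME-PTE instead of counting as a failure

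*SAP*

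**What the plan says.** **Missing EOT or PTE response.** SAP 7.3 makes a subject Indeterminate if the investigator cannot decide between success and failure "at the EOT or PTE Visits or the subject has a missing response", and then points to Table 4. Subjects with an "Indeterminate response are excluded from the CE-EOT, CE-PTE, ME-EOT and ME-PTE populations". Protocol 12.16 says that for PTE in the ITT population "subjects with missing data are assigned an Indeterminate response". Its Table 6 lists EOT Success with a missing PTE as Indeterminate, and likewise both visits missing.

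**Missing early clinical response (ECR).** Here failure comes first. SAP 7.3 treats the subject as missing "unless the subject is considered a Clinical Failure for another reason". SAP 5.2.1 says the same: "Assuming none of the above definitions of failure is met, the following cases will be considered an indeterminate response".

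**What counts as failure at PTE.** SAP 5.2.2.1 lists "The subject requires alternative antibacterial treatment for CABP prior to PTE related to" progression, new symptoms or infectious complications, and separately death before PTE. The estimand in SAP 5.2.2.2 counts rescue and death as failures for both ITT and CE-PTE.

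**Who belongs in CE-PTE.** SAP 6.1.4.3 does not exclude subjects given antibiotics because the test article was not effective enough. SAP 6.1.4.5 requires an overall response other than Indeterminate. It also requires a PTE visit 5 to 10 days after the last dose, waived for EOT failures "or the patient died after EOT and before PTE".

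**The concern.** Take a subject who was a Success at EOT, relapsed, was given alternative antibacterial treatment for CABP, and was then lost before PTE. This subject meets a PTE failure criterion and also the not-seen criterion for Indeterminate. SAP 5.2.2.1 does not rank the two. When the PTE field is blank, the missing-data rule settles the matter as Indeterminate. A death after EOT with a blank PTE response goes the same way.

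The subjects lost are all failures, so the omission can only raise CE-PTE and ME-PTE success rates. If such relapses or deaths are more frequent in one arm, it also shifts the treatment difference. Protocol 12.6.3 requires non-inferiority in both ITT and CE for the EMA conclusion, so the CE set is meant to be a check on ITT. It is a weaker check if documented failures can leave it.

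**Working it through.** **1. The plan's own figure.** Inputs from SAP 5.1.1: CE N = 0.80 × 670 = 536, or 268 per arm at 1:1; success 89% in both arms; margin 10%; one-sided alpha 0.025. (The text of Protocol 12.2 gives 80% for this rate, but its Table 4 and the SAP give 89%, which is the value that reproduces the stated power.) Farrington-Manning power is Φ[(0.10 − 1.96·s0)/s1].

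- Restricted estimates at a difference of −0.10: 0.8228 and 0.9228.
- s0 = √[(0.8228 × 0.1772 + 0.9228 × 0.0772)/268] = 0.02846.
- s1 = √(2 × 0.89 × 0.11/268) = 0.02703.
- (0.10 − 0.05578)/0.02703 = 1.636, so power is 94.9%, as stated. It does not depend on the present point.

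**2. The outcome rule.** Five of the nine cells in SAP Table 4 have at least one Indeterminate visit:

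| EOT | PTE | Overall at PTE |
|---|---|---|
| Failure | Indeterminate | Failure |
| Indeterminate | Failure | Failure |
| Success | Indeterminate | Indeterminate |
| Indeterminate | Success | Indeterminate |
| Indeterminate | Indeterminate | Indeterminate |

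The gap lies in the third and fifth rows, when the PTE response is missing and a rescue or death is documented.

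**3. Following such a subject through the SAP.**

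- Failure definition (5.2.2.1) and estimand (5.2.2.2): Failure.
- Missing-data rule (7.3 with Table 4): Indeterminate.
- CE-PTE, first bullet of 6.1.4.5: excluded, because the response is Indeterminate.
- CE-PTE, second bullet of 6.1.4.5: if there was no in-window visit, a rescued subject is excluded again, since the waiver names EOT failure and death but not rescue. A death passes this bullet but has already failed the first.
- SAP 8.1: its parenthetical allows a missed PTE visit in CE-PTE only for EOT failures. That omits even the deaths waived in 6.1.4.5.
- ME-PTE (6.1.5): excluded, because it requires CE-PTE membership.
- ITT: non-success in the denominator either way, so the rate does not change. In microITT the no-specimen microbiological response becomes Indeterminate instead of Presumed Persistence; it stays in the denominator, so the favourable rate does not change either.

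**4. Size, with assumed counts.** Planned CE failures are 268 × 0.11 = 29.5 per arm, and successes 268 × 0.89 = 238.5.

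If the planned 268 include k such failures and the rule removes them from one arm:

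- k = 3: 238.5/265 = 90.0%, up 1.0 point from 89.0%.
- k = 5: 238.5/263 = 90.7%, up 1.7 points.

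The other way round, suppose 239/268 (89.2%) is analysed in each arm and k omitted failures are put back into the omadacycline arm only. The unstratified Miettinen-Nurminen lower limit solves (p̂1 − p̂2 − RD)²/V = 3.84, with V as in SAP 9.1:

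| k | Omadacycline rate | Difference (points) | Lower 95% limit |
|---|---|---|---|
| 0 | 239/268 = 89.2% | 0.0 | −5.4% |
| 2 | 239/270 = 88.5% | −0.7 | −6.1% |
| 3 | 239/271 = 88.2% | −1.0 | −6.4% |
| 5 | 239/273 = 87.5% | −1.6 | −7.1% |
| 10 | 239/278 = 86.0% | −3.2 | −8.8% |
| 15 | 239/283 = 84.5% | −4.7 | −10.4% |

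**The case against.** The best defence is that EOT and PTE response are the investigator's own classifications, whereas ECR is derived by program and so needs a coded override. Protocol 8.13.1.3 obliges the investigator to choose one outcome. Indeterminate is for a response that could not be inferred, and documented rescue or death allows it to be inferred. A site that follows the definitions would enter Failure.

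This stands where the investigator does enter Failure: Table 4 then works, and the death waiver in SAP 6.1.4.5 keeps the subject in CE-PTE. It does not cover a blank field. The second limb of the SAP 7.3 sentence is written for a missing response, and it returns Indeterminate whatever else is on record.

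A reader might infer that every missing EOT or PTE response becomes Indeterminate with nothing to override it. The documents do not support that. Table 4, Protocol 12.6.2 and Protocol Table 6 carry an EOT failure forward, and a PTE failure prevails over a missing EOT. Nor is the death waiver without effect; it fails only when the response is also blank.

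The defence is also right that the Protocol 12.16 sentence on missing data is about ITT, where Indeterminate already counts as failure. Protocol Table 6, however, determines the PTE response itself, and Protocol 12.7 takes Indeterminates out of CE.

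**Conclusion.** The point holds for a defined group: Success, missing or Indeterminate at EOT, no investigator response at PTE, and rescue for CABP progression or complications, or death, documented before PTE. For them the stated rule contradicts the failure definition, the estimand, the rescue exemption in 6.1.4.3 and the evident intent of the death waiver.

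The size is unknown because the documents give no count. Under the assumption of 3 to 5 such subjects in one arm of 268, that arm's CE success is inflated by about 1.0 to 1.7 points of a 10-point margin. In the add-back illustration a one-arm excess of 10 still leaves the lower limit above −10%, and 15, about half the planned failures in an arm, takes it below. The documents also do not say whether the planned 89% already allows for these failures.

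It would be tempting to say that a non-inferiority conclusion is at risk. This SAP does not support that: its primary analysis is ECR in ITT, and SAP 9.3 makes the CE-PTE interval descriptive. CE is co-primary for the EMA under the protocol, but the EMA SAP is a separate document that was not available, and it may handle the case differently. The correction should be made before database lock. It does not touch the FDA primary analysis.

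**What to change.** 1. In SAP 7.3 and Table 4, and in Protocol 12.16 and Table 6, state that a missing or Indeterminate EOT or PTE response is Clinical Failure if death, or alternative antibacterial treatment for CABP progression or complications, is documented before that visit. If no PTE visit took place, apply this up to the end of the PTE window, 10 days after the last dose.
2. Extend the PTE-window waiver in SAP 6.1.4.5 to subjects rescued for CABP after EOT and before PTE, and let it apply also to an EOT failure derived under item 1. Align the parenthetical on missed PTE visits in SAP 8.1. Without this, item 1 alone leaves a rescued subject with no PTE visit outside CE-PTE.
3. Leave subjects given a potentially effective antibacterial for another infection as they are. SAP 6.1.4.3 excludes them from CE, and an override would not bring them back.
4. Carry the same rule into the EMA SAP.

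The cost is some wording and one derivation from mortality and antibacterial data that are already collected; SAP Appendix 3 already has rules for placing antibacterials relative to the EOT and PTE visits. CE success rates may come out slightly less favourable. The change is to the analysis only and alters no treatment.
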